1.0 SYNOPSIS

Title:	MultiPoint™ Pacing (MPP) Post Market Study
Acronym:	MPP PMS
Purpose:	The purpose of this post market study is to characterize real-world use of MPP technology in patients indicated for a cardiac resynchronization therapy (CRT) device.
Objectives:	
The primary objective of this post market study is to understand the use of the MPP technology in real-world clinical practice. The study should provide an understanding of the impact of MPP technology on:
 
 • Overall CRT response rate measured by Clinical Composite Score (CCS). (A responder is defined as improved or unchanged from baseline and non-responder is defined as worsened from baseline.) • Quality of Life (QOL), left ventricular ejection fraction (LVEF, if available) and left ventricular end systolic volume (LVESV, if available) • Programming timing and workflow • Rates of heart failure (HF) hospitalization events, cardiovascular hospitalizations, and HF 30-day hospitalization rates • Costs associated with HF-related health care utilizations • All-cause mortality
Design:	
This is a prospective, multicenter, non-randomized registry/observational study. The study will enroll up to 2,000 patients with successful SJM CRT MP device implant from up to 140 centers undergoing CRT implantation. Any patient who received a market approved SJM Quadra Allure MP, Quadra Assura MP, or newer SJM CRT MP device is eligible for enrollment in the study. MPP programming guidance will be specified in the protocol. Patients will be followed for 12 months after implant. Data will be collected at Baseline (within 30 days prior to implant), Post-Implant (within 30 days following successful CRT device implant), 3, 6, 12 months and during any unscheduled follow-up visit.
 
[REDACTED]

Devices used:	Market-approved SJM Quadra Allure MP, Quadra Assura MP device, or newer SJM CRT MP device and market-approved SJM Quadripolar LV lead
Study Population	All subjects who meet inclusion criteria, do not meet exclusion criteria, sign an IRB/EC approved informed consent, complete a Baseline visit prior to device implant and have an attempted implant of the SJM Quadra Allure MP, Quadra Assura MP, or newer SJM CRT MP device will be considered

[figure not shown]
Clinical Investigational Plan

	enrolled in the study.
Inclusion/Exclusion Criteria	
Inclusion Criteria Eligible patients will meet all of the following:
 
 • Are scheduled to receive a new CRT implant or an upgrade from an existing ICD/Pacemaker implant (SJM CRT MP device and SJM QUAD Lead) with no prior LV lead placement • Have the ability to provide informed consent for study participation and are willing and able to comply with the prescribed follow-up tests and schedule of evaluations 
Exclusion Criteria Patients will be excluded if they meet any of the following:
 
 • Are expected to receive a heart transplant during the duration of the study • Have an epicardial ventricular lead system (active or inactive) • Are less than 18 years of age • Are currently participating in a clinical investigation including an active treatment arm and belong to the active arm • Are not expected to complete the study follow-up schedule or duration due to any health condition other than heart failure, such as malignancy, indication for heart transplant or hospice care.
Data Collection	
All patients will complete a Baseline visit within 30 days prior to implant. During this visit, inclusion/exclusion criteria evaluation, informed consent, NYHA class, QOL questionnaires (Minnesota Living with Heart Failure – MLWHF and EQ-5D) will be completed. All subjects will undergo SJM CRT MP device implant per standard of care. Device measurements will be collected within 30 days of successful SJM CRT MP device implant during the Post-implant visit. Patients will be followed for 12 months after successful CRT implant. Follow-up data will be collected at 3, 6 and 12 months post implant and during any unscheduled follow-up visits. During the study mandated follow-up visits, arrhythmic episode diagnoses, device data, stored electrograms, LVEF (if available), LVESV (if available), NYHA class, Patient Global Assessment (PGA), and QOL questionnaires (Minnesota Living with Heart Failure – MLWHF and EQ-5D) will be collected. All clinical events for cardiovascular reasons, such as hospitalizations and emergency room visits, will also be collected. All study data, including device data and stored electrograms, will be sent to SJM via the electronic data capture (EDC) system.

Clinical Investigational Plan

1.1 STUDY FLOW CHART

*The implant procedure is not considered part of the research study.

Clinical Investigational Plan

2.0 BACKGROUND AND JUSTIFICATION FOR CLINICAL STUDY

Heart failure (HF) is a major threat to public health affecting an estimated 5.7 million individuals in the United States. It is estimated that 50% of people diagnosed with HF will die within 5 years.¹ In 2007, the direct and indirect cost for HF in the United States was estimated at \$33.2 billion.^{2,3} HF is a varied clinical syndrome with complex pathophysiology, which continues to be defined, and often begins with a primary insult to the myocardium. Patients with HF experience decreased exercise capacity, inability to perform activities of daily living, diminished quality of life and an increased early mortality.

Cardiac resynchronization therapy (CRT) using biventricular (BiV) pacing was developed to restore synchrony in HF patients with delayed ventricular activation, predominantly of the left ventricle (LV). Although a majority of treated patients show a benefit, up to 40% derive no benefit from CRT. In the MIRACLE study, 34% of patients did not demonstrate an improvement in a HF clinical composite score (CCS) that combined all-cause mortality, HF related hospitalization, NYHA class and patient global assessment into an outcome measure.⁴ Birnie and Tang summarized various clinical studies that report CRT non-responder rates.⁵ Rates of non-response to cardiac resynchronization therapy are often quoted as 20-30% in the listed studies, but the authors suggest the true non-responder rate may be as high as 40-50%. This inconsistent CRT effectiveness may be due to incomplete resynchronization and the presence of intraventricular dyssynchrony.

Although the cause for failed response to CRT is not completely understood, the consensus, supported by growing evidence, is suboptimal LV lead placement accounts for a large percentage of patients who do not respond to CRT. Standard LV lead placement criteria for a stimulation electrode typically focuses on the location of mechanical stability, freedom from phrenic nerve stimulation, reasonable pacing thresholds, or the site of latest electrical activation. However, ischemic cardiomyopathy can cause non-uniform propagation of electrical activity over the myocardium due to scarred myocardial segments and density near the LV stimulation electrode.⁶ Thus, a site of latest electrical activation may not always yield the optimal response. In such cases, the ability to pace from more than one left ventricular site may provide benefit.

The St. Jude Medical family of quadripolar leads includes one tip electrode and three ring electrodes. The Quartet™ LV family of leads with the CRT device provides 10 - 14 different pacing vector options (VectSelect™) from the four pacing electrodes on the LV lead. Since this CRT device can provide quadripolar pacing, the device and Quartet™ LV lead will be referred to as the Quadripolar CRT device system in this protocol.

Furthermore, this lead allows pacing from any two of the 10 - 14 available vectors that stimulate the LV in a multi-point fashion (MultiPoint™ pacing or MPP). In addition to the usual interventricular (RV-LV or V-V) timing that is currently available in a traditional CRT devices, MPP further allows timing between two LV lead pacing vectors termed 'LV1-LV2 timing' with programmable delays (5 – 80 ms).

MultiPoint™ pacing (MPP) is a new pacing feature in the Quadripolar CRT system that allows the LV with two pacing vectors compared to one vector in a traditional CRT system. A combination of any two of the 10 – 14 available vectors can be used. Additionally, a delay can be introduced between the two LV pacing vectors.

Clinical Investigational Plan

MPP via one LV lead has the potential to be an alternative to optimize LV lead placement non-invasively, and it is feasible the MPP feature may improve hemodynamics and the response to CRT. Studies showed simultaneously exciting a larger mass or volume of cardiac tissue results in faster depolarization velocity and shorter left ventricular trans-ventricular conduction times.^{7, 8} In addition, by capturing a larger volume of cardiac muscle, the site of latest intrinsic activation within the left ventricle may be more likely to be depolarized early, resulting in better synchronization and maximizing cardiac output.

Since MPP delivers two pulses at programmable delays (LV1 and LV2) to two LV sites, the initial volume of excited cardiac tissue is increased. Additionally, by capturing more mass at the initial depolarization, there is a greater likelihood of pacing the site of latest systolic delay. Both of these methods have shown to improve LV function⁹⁻²⁰ and it is believed this additional improvement in LV function may benefit those patients who are otherwise identified as non-responders to conventional BiV pacing.

Clinical Investigational Plan

3.0 STUDY DESIGN

3.1 Purpose

The purpose of this post market study is to characterize real-world use of MPP technology in patients indicated for a CRT device.

3.2 Study Design and Scope

This is a prospective, multicenter, non-randomized registry/observational study. All subjects who meet inclusion criteria, do not meet exclusion criteria, sign an IRB/EC approved informed consent, complete a Baseline visit prior to device implant and have an attempted implant of the SJM Quadra Allure MP, Quadra Assura MP, or newer SJM CRT MP device will be considered enrolled in the study. MPP programming guidelines are provided in Appendix I. Patients will be followed for 12 months after implant. Data will be collected at post-implant (within 30 days of successful CRT device implant), 3, 6, 12 months and during any unscheduled follow-up visit. At 12 months, the responder rate will be evaluated among the following groups:

- MPP Group: MPP ON within 1 month post implant and then continuously programmed ON until 12 months (i.e., MPP ON for months 1-12 continuously)
- Treatment Strategy (BiV/MPP) Group: MPP ON at the 12-month study visit and for at least 3 continuous months prior to 12-month assessment (i.e., BiV ON at some point in months 1-9 and MPP ON for months 10-12)
- BiV Group: MPP OFF at the 12-month study visit and for at least three continuous months prior to 12-month assessment (i.e., BiV ON for months 10-12)
- Other Pacing Group: Other pacing schemes not covered above (Retrospective categorization implemented based on the usage of MPP or BiV for 12 months)

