5.2 Evaluation of responder status

Patients' responder status will be assessed at 3, 6 and 12 months post implant using the CCS. The CCS includes four components: NYHA class, Patient Global Assessment (PGA), HF events, and cardiovascular death.²¹

The **NYHA Class assessment and PGA** are determined by a designated assessor interviewing patients about their symptoms. Specifically, the PGA will be a single interview question asking the patient to categorize how they feel compared to their previous visits as either:

- Markedly better
- Better
- No change
- Worse
- Markedly worse

At the 3, 6 and 12-month visits, a PGA will be conducted to evaluate how the patient feels compared before having the CRT system implanted.

In this trial, a **HF event** is defined as any one of the following when the subject has symptoms and/or signs consistent with congestive heart failure:

- Hospitalization for HF \geq 24 hours
- Clinic or hospital visit for HF < 24 hours (i.e. outpatient treatment, observational care, ER, Urgent Care and physician's office visit) requiring administration of IV diuretics, inotropes, and/or vasodilators

Finally, **cardiovascular death** is defined as sudden unexpected death; heart failure death; myocardial infarction related death; or 'other' death, such as deaths due to pulmonary embolism, peripheral thromboembolism, stroke, vascular procedure, or other major cardiovascular event.

Using the CCS and decision algorithm described in section 5.2.1 patients are categorized as Improved, Worsened or Unchanged based on the following rules:

- “Improved” – patients demonstrating:
 - At least a one-class improvement in NYHA Class OR improvement by PGA (“better” or “markedly better”)
AND
 - No HF events as described above
AND
 - No cardiovascular death
- “Worsened” – patients demonstrating:
 - Worsening in NYHA Class OR worsening by PGA (“worse” or “markedly worse”)

OR

[figure not shown]

Clinical Investigational Plan

- Presence of HF events as described above
OR
 - Cardiovascular death
- “Unchanged” – patients neither “Improved” nor “Worsened”.

Patients who are “Improved” or “Unchanged” using the above definition will be grouped together as Responders. Patients classified as “Worsened” will be considered Non-Responders.

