12.1 STATISTICAL DESIGN, HYPOTHESES, METHOD AND ANALYTICAL PROCEDURES

This is a prospective, multicenter, non-randomized registry/observational study. Analysis of the study objectives will be summarized using data collected upon 12-month follow-up visit by the groups defined in section 3.2. The objectives of this study will be summarized as the follows:

- Overall CRT response rate at 12 months will be summarized by percentages with a 95% confidence interval using exact method for binomial distribution.
- QOL, LVEF, and LVESV at baseline, 3, 6, and 12 months will be summarized by means (\pm standard deviation), median and range.
- Programming timing and workflow between implant and 12 months will be summarized by frequency and percentage for categorical data.
- Rates of heart failure (HF) hospitalization events at 12 months, cardiovascular hospitalizations at 12 months, and HF 30-day hospitalization rates will be summarized using Kaplan-Meier method.
- Costs associated with HF-related health care utilizations at 12 months will be summarized by means (\pm standard deviation), median and range.
- All-cause mortality at 12 months will be summarized using Kaplan-Meier method.

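### The BiV and BiV/MPP Groups, and on its plain wording the MPP Group, admit only patients who reach 12 months, yet mortality, hospitalization, cost and CCS are summarised by these groups

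*Combined protocol and SAP*

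**What the plan says.** Section 3.2 sorts patients into four pacing groups, introduced there for the 12-month responder rate:

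- MPP Group: "MPP ON within 1 month post implant and then continuously programmed ON until 12 months", explained as MPP ON throughout months 1 to 12. The 12-month visit is not named.
- Treatment Strategy (BiV/MPP) Group: "MPP ON at the 12-month study visit and for at least 3 continuous months prior to 12-month assessment".
- BiV Group: "MPP OFF at the 12-month study visit and for at least three continuous months prior to 12-month assessment".
- Other Pacing Group: "Other pacing schemes not covered above (Retrospective categorization implemented based on the usage of MPP or BiV for 12 months").

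Section 12.1 extends the groups beyond response: "Analysis of the study objectives will be summarized using data collected upon 12-month follow-up visit by the groups defined in section 3.2". The list that follows includes CCS response, HF and cardiovascular hospitalization by Kaplan-Meier, HF-related cost, and mortality: "All-cause mortality at 12 months will be summarized using Kaplan-Meier method". Section 6.1 separately plans to compare costs among the same groups.

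On the CCS, section 5.2 states: "The CCS includes four components: NYHA class, Patient Global Assessment (PGA), HF events, and cardiovascular death". A cardiovascular death makes the patient Worsened and so a Non-Responder.

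No visible text says which group a patient belongs to if he or she dies before the 12-month visit.

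**The concern.** Group membership is fixed by what happens up to 12 months, and the outcomes are counted over those same 12 months. Where membership requires survival to the end of the counting period, a death cannot be recorded in the group. Kaplan-Meier censoring does not repair this, because the patients who died were never group members.

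Section 3.3 lists the impact of MPP on all-cause mortality among the things the study should clarify. If the groups are used as written, the mortality table for the named pacing modes is settled before any data are collected. The CCS loses one of its four components in those groups. Hospitalization and cost are described only in patients who survived, so admissions and costs before a death drop out.

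**Working it through.** There is no planned figure to reproduce: the sample-size text in section 12.2 is redacted and no event rates are given. The main check is logical; the sizes below are illustrations on stated assumptions.

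**1. Where does a patient who dies in month 5 go?**
- BiV and BiV/MPP: each needs a programming state at the 12-month visit. Not met.
- MPP: needs MPP ON through month 12. Not met on the plain wording.
- Other: takes schemes not covered elsewhere, but categorises on 12 months of usage, which this patient does not have. So the patient falls in Other or in no group.

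**2. Mortality.** To the 12-month visit, deaths in a named group are 0 of n, so the Kaplan-Meier estimate is 0% at any true rate. The result would also look precise. The exact 95% upper limit with no events is 1 − 0.025^(1/n): 0.74% for an assumed n = 500 and 0.37% for n = 1,000. The visit window of ±45 days (section 5.5) does not help, because safety surveillance ends at the last visit (section 9.2).

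**3. CCS response.** Let R be response among survivors and c the proportion with cardiovascular death among patients with a CCS classification. The named groups show R. With cardiovascular deaths kept as Non-Responders, response is R(1 − c). The excess is R − R(1 − c) = R × c.

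| c (assumed) | R = 70% | R = 85% |
|---|---|---|
| 2% | 1.4 points | 1.7 points |
| 5% | 3.5 points | 4.25 points |
| 8% | 5.6 points | 6.8 points |

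**4. The Other group, if it takes every early death.** With true 12-month mortality m and a share o of survivors in Other, its mortality is m / (m + (1 − m)o). For m = 5% and o = 10%: 0.05 / (0.05 + 0.095) = 34.5%. Over m = 3-10% and o = 5-20% the result runs from 13.4% to 69.0%. These are not bounds: m = 3% and o = 35% gives 0.03 / (0.03 + 0.3395) = 8.1%.

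**5. Does it favour MPP?** A simulation of 4,000,000 patients assumed no pacing effect, half starting with MPP ON, at most one switch (20% over 12 months), cardiovascular death 5%, other death 2% and survivor response 78%. All early deaths were placed in Other. MPP, BiV/MPP and BiV each showed 0.0% mortality and 77.9-78.0% response. The whole cohort showed 6.9% and 74.1%. The three named groups are distorted alike.

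**6. Hospitalization and cost.** The documents give nothing from which to size this. Its direction depends on how often patients who died were admitted before death.

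**The case against.** The strongest reply is that this is a descriptive registry meant to characterise use of MPP. Section 12.1 contains no visible hypothesis or success criterion, section 3.2 brings in the groups only for response, and the mortality line names no group. What stands is that the harm is confined to descriptive by-group results and that no error rate is at stake. What does not stand is that the groups serve response alone: the opening sentence of section 12.1 covers the objectives generally, section 6.1 applies the groups to cost, and response is itself affected through the cardiovascular-death component.

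A second reply is that text we cannot see (section 12.2, part of the synopsis design paragraph, the decision algorithm in 5.2.1) may deal with deaths. That cannot be excluded. But sections 3.2 and 12.1, where a rule for assigning deaths to groups belongs, are visible and contain none.

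Three stronger readings are tempting and are not supported:
- That the design builds in an advantage for MPP over BiV. On the plain wording all three named groups are conditioned on survival alike. A spurious difference arises only if the MPP Group alone admitted deaths after month 1. At an assumed 5% mortality with a constant hazard, month-1 survival is 0.95^(1/12) = 0.9957, and MPP would show (0.9957 − 0.95) / 0.9957 = 4.6% against 0% in BiV. That would count against MPP, and it is not what the definition says.
- That every early death lands in Other. The retrospective 12-month usage condition leaves room for some to belong to no group.
- That the study's overall results are invalid. Whole-cohort figures do not depend on the groups.

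**Conclusion.** The point holds and should be fixed. Mortality to the 12-month visit is 0% by definition in the BiV and BiV/MPP Groups, and in the MPP Group on its plain wording. This needs no assumption about event rates. Consequently the mortality objective cannot be answered by these groups.

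The overstatement of response in step 3 is real in direction, but its size rests wholly on assumed rates, as do the percentages for Other. It should be treated as a main defect of the by-group descriptive tables, not as a threat to the registry as a whole.

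**What to change.** Edit sections 3.2, 6.1 and 12.1.

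1. **Mortality.** Do not report it by the section 3.2 groups; report it for the whole cohort.
2. **Mortality and hospitalization by pacing mode.** Take patients alive at day 30 after successful implant and group them by the mode in the last device session record on or before day 30. Start the clock at day 30, keep later deaths in their group, censor withdrawals, and report how many patients have no record. Report earlier events for the whole cohort. As a supportive analysis, treat MPP ON/OFF as time-varying from the session records. State that both are open to confounding by indication. Do not rank them on simulation: in the available runs the initial mode was independent of risk, so they cannot show confounding at the first programming choice.
3. **Section 3.2 groups.** Keep them for programming patterns, CCS response and the section 6.1 cost comparison, labelled as conditional on reaching the 12-month visit. Beside them give CCS and cost by day-30 mode, with patients who died included. Leave the section 5.2 CCS unchanged: HF events count from implant, and cardiovascular death is Non-Responder.
4. **Deaths from other causes without a 12-month CCS.** Use one rule by group and in the whole cohort: Worsened if an HF event occurred; otherwise excluded from the denominator, with the count given. They should not default to Unchanged. In the simulation that default would raise whole-cohort response from 74.1% to 74.6%.

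**Cost.** Wording and extra programming, with no new visits or data items. Day-30 groups mix in later switchers and do not show the Treatment Strategy Group separately. The post-implant visit may fall on the day of implant (section 5.4.4), so some patients may have only that record, and later changes appear only if unscheduled-visit records are sent (section 5.6). HF events before day 30 may have influenced the day-30 mode. Confounding by indication remains, because programming is left to the physician (section 5.5).

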3.3 Objectives

The objective of this post-market study is to understand the use of the MPP technology in real-world clinical practice. The study should provide an understanding of the impact of MPP technology on:

Clinical Investigational Plan

- Overall CRT response rate measured by CCS. (A responder is defined as improved or unchanged from baseline and non-responder is defined as worsened from baseline.)
- QOL, LVEF, if available and LVESV, if available
- Programming timing and workflow
- Rates of HF hospitalization events, cardiovascular hospitalizations, and HF 30-day hospitalization rates
- Costs associated with HF-related healthcare utilizations
- All-cause mortality

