6.1 HEALTH CARE ECONOMIC DATA

To assess potential differences in costs for heart failure-related health care utilizations among the groups described in section 3.2, billing records (i.e., UB-04 and CMS-1500 for centers in the United States) will be collected on a Health Care Utilization/ Hospitalization CRF.

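### Section 3.2 pacing groups are set in retrospect under unequal rules, so unadjusted MPP and BiV summaries can differ without an MPP effect, and deaths before month 12 have no stated place

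*Combined protocol and SAP*

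**What the plan says.** Section 3.2 defines four groups for the 12-month evaluation and says that the categorisation is retrospective.

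- **MPP Group:** "MPP ON within 1 month post implant and then continuously programmed ON until 12 months".
- **Treatment Strategy (BiV/MPP) Group:** "MPP ON at the 12-month study visit and for at least 3 continuous months prior to 12-month assessment", with BiV at some point in months 1 to 9.
- **BiV Group:** "MPP OFF at the 12-month study visit and for at least three continuous months prior to 12-month assessment". Nothing is required of months 1 to 9.
- **Residual group:** "Other Pacing Group: Other pacing schemes not covered above".

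Section 5.5 leaves the choice between BiV and MPP to the physician at every visit. Section 5.2 assesses the Clinical Composite Score (CCS) at 3, 6 and 12 months and counts HF events and cardiovascular death as worsening, that is, as non-response.

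Section 12.1 states: "Analysis of the study objectives will be summarized using data collected upon 12-month follow-up visit by the groups defined in section 3.2". The methods listed are percentages with exact intervals, means, medians and ranges, and Kaplan-Meier estimates. No adjustment appears in the visible text. On mortality it says: "All-cause mortality at 12 months will be summarized using Kaplan-Meier method".

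The study's purpose (section 3.1) is to characterise use. Section 3.3 goes further: "The study should provide an understanding of the impact of MPP technology on" response, hospitalisation, cost and mortality. Section 6.1 collects billing records "To assess potential differences in costs for heart failure-related health care utilizations among the groups described in section 3.2".

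**The concern.** There are two separate problems.

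**Group membership can depend on the outcome.** Response is assessed at 3 and 6 months, before the group is fixed, and the physician may reprogram at any visit. A patient who does badly on MPP and is switched off by about month 9 leaves the MPP Group and is counted as BiV. A patient who does badly on BiV and is switched to MPP leaves the BiV Group for BiV/MPP. The MPP Group therefore keeps only patients who stayed on MPP, while the BiV Group mixes patients who stayed on BiV with patients who came off MPP. If switching is related to early response, the MPP and BiV responder rates differ even when the pacing mode does nothing.

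**Early deaths have no stated place.** BiV and BiV/MPP are defined by status at the 12-month visit, and MPP must run until 12 months. Taken literally, someone who dies in month 7 meets none of these rules and falls to Other Pacing. The responder rates of the named groups would then describe survivors only, and their Kaplan-Meier mortality before the 12-month visit would be zero whatever happened to patients on each mode.

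At stake is how the main tables are read. With objectives worded as impact and as cost differences among the groups, readers will set MPP beside BiV.

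**Working it through.** The plan gives no figure to reproduce: section 12.2 is redacted and no group difference is predicted. The check asks whether the section 3.2 rules can create a difference when pacing mode has no effect at all.

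**Inputs (all assumed; none is in the documents).** Half of patients start on each mode. Early failure is 20% on either mode. Of those without early failure, 5% worsen later. Every early failure still counts as non-response at month 12. Switching is 50% after early failure where it responds to outcome, and 5% otherwise. All switches come early enough to meet the three-month rules. Nobody dies.

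**Per unit of patients starting on a given mode:**

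- With 50% switching after failure, stayers are 0.20 × 0.50 + 0.80 × 0.95 = 0.10 + 0.76 = 0.86. Switchers are 0.10 + 0.04 = 0.14.
- With 5% switching after failure, stayers are 0.20 × 0.95 + 0.76 = 0.95. Switchers are 0.05.
- Responders among stayers are 0.76 × 0.95 = 0.722, and among switchers 0.04 × 0.95 = 0.038, in both cases.

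The MPP Group is the MPP stayers. The BiV Group is the BiV stayers plus the MPP-to-BiV switchers. Because half start on each mode, the weights cancel.

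| Switching after failure | MPP Group | BiV Group | Gap (points) | BiV throughout | Gap after separation |
|---|---|---|---|---|---|
| 5% from both modes (unrelated to outcome) | 0.722/0.95 = 76.0% | 0.760/1.00 = 76.0% | 0.0 | 76.0% | 0.0 |
| 50% from both modes | 0.722/0.86 = 84.0% | 0.760/1.00 = 76.0% | +8.0 | 84.0% | 0.0 |
| 50% from MPP, 5% from BiV | 84.0% | 0.760/1.09 = 69.7% | +14.2 | 0.722/0.95 = 76.0% | +8.0 |
| 5% from MPP, 50% from BiV | 76.0% | 0.760/0.91 = 83.5% | -7.5 | 84.0% | -8.0 |

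The true response is 0.80 × 0.95 = 76.0% for both modes in every row, so each non-zero gap is selection. The sign depends on which switch follows failure. Separating the MPP-to-BiV switchers makes the two definitions alike and removes the gap when switching is symmetric. When it is one-sided, a gap remains; in the last row it is slightly wider. If early failure had no bearing on the 12-month score, all gaps would vanish.

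**Deaths.** Assume 80% response among survivors and 12-month cardiovascular mortality of 2%, 5% or 10% in a named group. With deaths sent to Other Pacing, the group shows 80.0% each time. With deaths kept in the group as non-responders it shows 0.98 × 0.80 = 78.4%, 0.95 × 0.80 = 76.0% or 0.90 × 0.80 = 72.0%. Equal mortality shifts every named group equally; unequal mortality would be hidden. On the literal rule the Kaplan-Meier curves of the named groups cannot fall before the 12-month visit.

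**The case against.** The strongest reply is that this is a declared non-randomised registry meant to describe use. It is open about retrospective categorisation, and the visible text plans no test and no estimated difference. That is right, and it limits the point to interpretation. A reader might infer a failed hypothesis test or an inflated error rate; the documents support neither.

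Second, outcome-driven switching is not documented. Section 2.0 states a belief that MPP may help patients who do not respond to BiV. Section 8.0 says that MPP can be disabled where it does not benefit a patient, but in the context of battery life. Neither describes a switching practice. A reader might infer that the groups are known to be biased, or biased in favour of MPP by a typical amount. The documents do not support that: size and sign are unknown, and the cases above were chosen to show the mechanism.

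Third, the literal reading of deaths is probably not intended. Kaplan-Meier mortality by group would be pointless if the named groups could hold no early death, and section 9.3.1 already asks for the device configuration at death. A reader might infer that mortality in the named groups will be zero. That follows only on the literal reading. What stands is that no rule is written, so two analysts could produce different tables.

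**Conclusion.** The point holds as one of interpretation and missing definition. The unequal rules, the discretionary programming and the unadjusted summaries are plain on the text. Together they allow MPP and BiV summaries to differ in either direction with no MPP effect, provided that switching is related to early response and early response carries through to the 12-month score. If either condition fails, this bias is absent. The 84.0% against 76.0% example shows that the mechanism can matter; it is no forecast for this study.

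The gap on deaths does not depend on switching. Read literally, the three named groups exclude every death before the 12-month visit, which conflicts with counting cardiovascular death as non-response and with summarising 12-month mortality by these groups. The literal reading is unlikely to be meant, so this is a rule to be written down. Both matters are worth correcting because the remedy is small and uses data already collected.

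**What to change.** 1. **Sections 3.2 and 12.1:** report patients switched from MPP to BiV separately from patients on BiV throughout. This puts the MPP and BiV definitions on the same footing. It reduces selection by switching overall but does not remove it, and the continuous-BiV group becomes smaller.

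2. **Sections 3.2 and 12.1:** state that patients who die before month 12 are placed by last recorded programmed mode, with earlier programming deciding between the continuous and the switched rows. Use the device configuration at death (section 9.3.1) and the downloaded programming records (sections 5.4.4, 5.5 and 5.6). Apply one rule to both the CCS and the Kaplan-Meier mortality summary. Section 9.3.1 asks for the configuration only if available, so list deaths with no recorded mode separately.

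3. **Sections 3.2, 6.1 and 12.1:** state that differences among the groups are descriptive and are not estimates of an MPP effect.

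Optionally, add a sensitivity table by programmed mode at the Post-Implant visit, regardless of later switching. It needs a note that confounding in the initial choice remains. For example, assumed early failure of 25% in MPP starters and 20% in BiV starters gives 0.75 × 0.95 = 71.25% against 76.0%, or -4.75 points, with no MPP effect. It is also diluted by crossover: with 14% switching each way, about 1 - 0.14 - 0.14 = 72% of any effect of final mode remains.

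The cost is wording in three sections and an extra row in the group tables, plus one table if the option is taken. No new visit, data item or change to programming is needed.
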